Detailed instructions for use of the device are available here: https://www.storzbickel.com/media/wysiwyq/CRAFTY-MIGHTY/PDF/mighty-vaporizer-instructions-manual.pdf (see annex documents) and are provided in the supplementary materials section of the IRB application. Participants will inhale the contents of one Mighty Medic dosing capsule. Specifically, they will be given 15 minutes to inhale the contents of the capsule ad libitum (i.e., at their own pace). Participants will take a minimum of 15 puffs, and if a visible vapor is still observed after 15 puffs, they will continue to take puffs until they no longer exhale visible vapor (this signifies that the dosing capsule is depleted; see detailed instructional materials from Stortz and Bickel). Following each puff, participants will exhale vapor into a hand-held smoke filter; this will ensure that neither the study participants or research staff see the exhaled vapor. We have found in our ongoing study with a different terpene (limonene) that the visibility of exhaled vapor can differ between pure THC, pure terpenes, and placebo. Overall, the puffing procedure will produce THC exposure of 0 or 30mg THC, and alpha-pinene exposure of 0.5mg, 5mg, or 15mg. Participants will be able to halt self-administration of the study drug if they experience adverse effects prior to inhaling the entire dose. Similarly, study staff may halt the drug administration procedure if untoward drug effects are observed. This is not expected at the doses under investigation, but may occur in rare circumstances. Study participants and research staff will be blinded to dose assignment. The conclusion of drug administration will be considered the "0 hour" by which remaining protocol assessments will be scheduled. To prevent issues of crosscontamination, new dosing pods and mouthpieces will be used for every test session, and the vaporizer will be disassembled and thoroughly cleaned according to manufacturers recommended methods between study participants.

Post-Drug Administration Procedures.

Following the "0-hour" time point (last exhalation of study drug), participants will complete a battery of assessments that includes:

- 1) Serum specimen collection at 0min, 15 min, 60 min, 120 min, and 180 min.
- 2) Subjective drug effect and mood ratings on computerized questionnaires and vital signs assessments at 0 min, 15 min, 30 min, 60 min, 90 min, 120 min, 180 min, 240 min, 300 min, and 360 min.

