- 3) Cognitive performance tests at 0, 30 min, 60 min, 90 min, 120 min, 180 min, 240 min, 300 min, and 360 min (Episodic memory tests will only be administered at 30 min and 360 min).

Use of medication or tobacco products will not be allowed during the study sessions. Study participants who regularly use tobacco products will be provided a nicotine patch upon request.

Outpatient Discharge. Participants will be discharged after completing final assessments (approximately 6 hours post-exposure). In prior studies conducted in our laboratory, this timeline has been adequate for healthy adults to resolve any effects from acute doses of cannabis that are similar to those used in the present protocol. If a study participant indicates the desire to be discharged from the study early, BPRU medical staff will review the self-reported rating of "drug

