effect" on the most recent subjective drug effect assessment, performance on the cognitive test battery, and conduct a brief interview with the participant prior to discharge. At the end of each session, study staff will compare vital signs and cognitive performance assessments with baseline data and engage in face-to-face conversation with the participant to ensure that they are fit to leave the unit. Cognitive performance tasks obtained measure psychomotor ability, working memory, higher-order cognitive functioning and attention. If the participant is able to cognitively engage with staff, vital signs are within normative range (HR < 100bpm, SYS BP < 150mmHg, DIA BP < 90mmHg), and performance is not below 20% of baseline, the participant will be cleared to leave without further evaluation. If any of these parameters are not met, medical staff will assess the participant and a formal field sobriety test will be conducted. Note, that multiple members of the BPRU cannabis lab have received formal training on administering filed sobriety tests by a Maryland State Police Drug Recognition Expert (DRE). If the participant reports a drug effect or exhibits behavior indicative of impairment/intoxication, the participant will be asked to remain at the BPRU until the drug effect subsides and they can pass a field sobriety test. If vital signs are out of range, then medical staff will evaluate and make a determination with regards to whether it is safe for participant to be discharged or remain under observation. Participants will not be allowed to drive home; instructions will be provided at the screening session regarding the need to make alternative transportation arrangements. If a participant fails to arrange a ride, taxi transportation home will be coordinated by study staff and provided free of charge.

For ease of scheduling, we will target conduct of sessions on a weekly basis. Because there are 6 total sessions, some participants may want to complete at an accelerated rate. A minimum of 48 hours will separate each study session and no more than 2 sessions will be completed in a calendar week. These timing parameters will allow for adequate elimination of study drugs between sessions and keeps the frequency of exposure to acceptable levels given that the study population will be infrequent cannabis users at the time of study participation.

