A 21-item Drug Effect Questionnaire will be used to obtain subjective ratings of intoxication. Individual items include ratings of drug effects (i.e. drug effect, pleasant drug effect, unpleasant drug effect) and behavioral/mood states often associated with cannabis intoxication (i.e. relaxed, paranoid, hungry/have munchies). Participants will rate each item using a 100mm visual analog scale (VAS) anchored with "not at all" on one end and "extremely" on the other. At the end of each session, participants will also complete a brief hypothetical purchasing questionnaire in which they estimate how much they would purchase of the dose they just received if it were to cost different prices.

The Profile of Mood States (POMS) questionnaire is a 65-item questionnaire that is commonly used to assess state-dependent changes in mood on 7 different domains: anger-hostility, confusion-bewilderment, depression-dejection, fatigue-inertia, tension-anxiety, vigor-activity, and friendliness.

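### The cognitive criterion for discharge, read literally, lets a participant leave after losing up to 80% of baseline performance; a 20% loss was very probably meant

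*Combined protocol and SAP*

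**What the plan says.** Section 4.a, Outpatient Discharge, has staff compare vital signs and cognitive test results with baseline at the end of every session and talk with the participant face to face. The stated purpose is "to ensure that they are fit to leave the unit".

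Release without further evaluation needs three things together: the participant can engage cognitively with staff; heart rate and blood pressure are within stated numeric limits; and, for the test battery, "performance is not below 20% of baseline, the participant will be cleared to leave without further evaluation".

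Failing any one has a defined consequence: "If any of these parameters are not met, medical staff will assess the participant and a formal field sobriety test will be conducted".

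Two further protections stand apart from the numeric criterion: "If the participant reports a drug effect or exhibits behavior indicative of impairment/intoxication, the participant will be asked to remain at the BPRU", and "Participants will not be allowed to drive home".

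The threshold is not restated anywhere else in the document.

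**The concern.** Falling below 20% of baseline means scoring under one fifth of the baseline score. A participant who keeps just one fifth, and so has lost four fifths, meets the criterion. This is the only numeric cognitive limit in the discharge text, and it stands beside exact limits for heart rate and blood pressure. The natural reading is that a decrement of 20% was meant and that the words turned it into a floor of 20%.

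What is at stake is participant safety. The sentence is part of the rule that decides who leaves without a medical assessment and a field sobriety test, in a study that gives 30 mg of inhaled THC to infrequent users. The test battery is the objective part of the cognitive check; engagement with staff, reported drug effect and observed behaviour rest on self-report or judgement. At the literal threshold the battery would almost never stop anyone.

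**Working it through.** The protocol states the threshold without deriving it, so there is no sponsor calculation to reproduce. The check sets the two readings side by side.

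**Inputs**
- Threshold: 20%, section 4.a, Outpatient Discharge.
- PASAT maximum: 90 correct, section 4.a, Study Measures.
- Illustrative PASAT baselines: 75 to 90. The 75 is the example competency score in section 5, inclusion criterion 9, and 90 is the maximum. Using this range for a session baseline is an assumption.
- Drop after 30 mg pure THC: a mean of about 10 correct responses, which section 6.a describes as moderate impairment of working memory.
- Conditions and completers: 6 conditions, 4 of them containing 30 mg THC, and 20 completers, section 4.a, Protocol Overview.

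**Formulas**
- Literal reading: floor = 0.20 × baseline; loss that still passes = 0.80 × baseline.
- Probable intended reading: floor = 0.80 × baseline; loss that still passes = 0.20 × baseline.

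| Assumed PASAT baseline | Literal floor | Loss that passes | Probable intended floor | Loss that passes | Gap between floors |
|---|---|---|---|---|---|
| 75 | 0.20 × 75 = 15 | 75 − 15 = 60 | 0.80 × 75 = 60 | 75 − 60 = 15 | 60 − 15 = 45 |
| 90 | 0.20 × 90 = 18 | 90 − 18 = 72 | 0.80 × 90 = 72 | 90 − 72 = 18 | 72 − 18 = 54 |

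The percentages do not depend on the assumed baseline: the literal rule passes a loss of 80% at any starting score, and its floor is one quarter of the probable intended one (0.20 / 0.80).

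**Against the protocol's own scale of impairment.** A drop of 10 is 10/75 = 13% to 10/90 = 11% of baseline. The literal rule tolerates 60/10 = 6 to 72/10 = 7.2 times that drop.

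**How often the rule is used.** Among completers, 20 × 6 = 120 planned session ends, of which 20 × 4 = 80 follow a dose containing 30 mg THC. Sessions of participants who drop out and repeated sessions come on top. These are uses of the rule over the whole study, not a measure of risk.

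**The case against.** The strongest reply is that this is loose wording whose sense is obvious, and that the rest of the discharge procedure protects the participant anyway. For the literal reading to release someone impaired, that person would have to converse normally, have vital signs in range, report no drug effect and show no sign of intoxication. The schedule that begins "Subjective drug effect and mood ratings on computerized questionnaires and vital signs assessments at 0 min" runs to 360 minutes, and on the questionnaire "Individual items include ratings of drug effects", so self-reported effect is recorded close to discharge. Anyone reporting or showing an effect is held whatever the test scores. Nobody drives home. On the 6-hour stay, the protocol adds that in earlier studies at the same laboratory "this timeline has been adequate for healthy adults to resolve any effects from acute doses of cannabis", at similar doses. Nothing in the document shows staff applying the literal threshold.

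All of this stands, and it keeps the practical risk low. It does not make the criterion right: a release rule should not depend on staff reading it against its words.

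A second objection is that the intended figure is inferred. That also stands. The literal floor is a matter of arithmetic; the 20% decrement is only the most plausible intention.

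A third is that the corrected rule would still pass a PASAT drop of 15 to 18, more than the 10 or so that the protocol calls moderate impairment. That is true. It is a reason for the investigators to consider a tighter limit, not a reason to keep a floor four times lower.

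**Conclusion.** The concern holds. As written, the cognitive discharge criterion accepts a loss of up to 80% of baseline and cannot do the job assigned to it. If a 20% decrement was meant, the two readings differ by 45 to 54 correct responses out of 90 on the PASAT, for assumed baselines of 75 to 90.

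The literal meaning is certain. The intended meaning is very probable but unconfirmed. This is an error of wording in a safety rule that should be corrected. Other safeguards limit its practical consequence, and it does not touch the sample size, any endpoint or the analysis.

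**What to change.** Replace the phrase in section 4.a, Outpatient Discharge, with: *performance is not more than 20% below that session's pre-dose baseline*. The investigators should confirm that 20% is the decrement they intend.

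Two details belong with it:
- **Which baseline.** The protocol uses the word both for the pre-dose assessments of each session (Baseline Assessments) and for the trained level reached at screening (Study Measures). Naming the session's pre-dose value settles this.
- **Which tasks.** Apply the rule to tasks that have a pre-dose score, for example PASAT and DSST total correct. List recall should be left out, because the first list is shown before dosing and recall is scored only afterwards. If measures such as reaction time are included, state that a higher value counts as worse. State also whether one failed task is enough to trigger evaluation.

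The core change is one phrase. The pre-dose battery and the 360-minute tests already supply the scores, so no new data are needed. The cost is that a few more participants may need a medical assessment and a field sobriety test before they leave.

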Experimental Session Procedures. For all study sessions, participants will be scheduled to arrive at approximately 8:00 in the morning on the day of cannabis exposure. Until such time as Covid-19-related restrictions on day-to-day operations are no longer required, social distancing will be maintained to the extent possible and all staff and study participants will be required to wear PPE throughout all face-to-face interactions. This will include mandatory use of face

masks and, when closer than 6ft, use of face shields and disposable gloves. Participants will be provided PPE by study staff as necessary.

All participants will complete a breath alcohol test on arrival. Urine drug and pregnancy testing will then be conducted for all participants to test for evidence of recent illicit drug use (e.g. cannabis, cocaine, opioids) and pregnancy. Participants with a positive BAL or urine drug screen positive for any drug except THC will be sent home and the session re-scheduled. Participants who have a 2nd positive BAL, 2nd positive urine drug screen or confirmed positive pregnancy test will be immediately discharged from the study. The Time Line Follow Back (TLFB) procedure will be conducted to record substance use since the last study visit (intake assessment or prior experimental session). Concomitant medications, including vitamins and herbal supplements taken within 14 days prior to the first experimental session and throughout study participation will be recorded. Changes in medication occurring between the screening assessment and first experimental session, or between subsequent experimental sessions will be reviewed by a study investigator and medical staff prior to starting the session to ensure the volunteer is still eligible to participate.

Baseline Assessments. Prior to drug administration, the following baseline assessments will be completed: 5mL serum blood sample, vital signs (HR, BP), subjective drug effect questionnaire, and a brief cognitive performance battery including tests of working and episodic memory (see below for details).

Experimental Drug Exposure.

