Finally, we will assess episodic memory impairment using a simple delayed verbal recall task called the international shopping list test (Thompson et al. 2011). Performance on this test has been shown to decrease as a result of cannabis exposure in prior controlled studies (Bidwell et al., 2018). In this task, participants are shown a 12-item grocery list and asked to recall as many items from that list as possible at a later time. In each condition of the present study, participants will be shown such a list at baseline (before drug administration) and will be asked to recall items from the list post-drug administration (during peak drug effects). Following recall of the initial list, participants will be presented with a new list of 12 items that they will be asked to memorize. Recall of this second list will be measured at the end of the experimental session (6 hours-post dosing). The second list will contain non-grocery store items to avoid confusion with the first list. Testing verbal recall twice in this manner (once during peak drug effects, once

again at the end of the session) will allow us to test whether pinene mitigates THC-induced memory impairment at two memory stages: the memory retrieval phase (list 1) and the memory encoding/consolidation phase (list 2). Participants will be presented with new lists at each experimental session.

b. Study duration and number of study visits required of research participants.

Eight study visits will be required. One visit for screening evaluation, and 6 outpatient experimental sessions lasting approximately 7 hours each. Because there are so many experimental testing sessions in this trial, and interpretation of data is contingent on a complete data set, participants may be invited to repeat a study session should circumstances arise that result in the loss of data during a session (e.g., failure to obtain blood specimens or missing cognitive testing time points), or protocol deviation that impacts data integrity. This is not expected to occur for most participants. Because the study involves repeated collection of blood samples, participants may not repeat more than 4 testing sessions, as this would result in cumulative blood collection that would exceed what is typically collected during a single routine blood donation (473mL); see Risks, Section 7, below. That said, it would be very unlikely for a participant to repeat more than 1 test session.

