THC is FDA approved as an oral formulation (dronabinol; Marinol). Pinene is Generally Recognized as Safe (GRAS) for oral consumption. Neither THC or pinene is FDA approved via the pulmonary route. As detailed above, we believe that the THC and pinene administration in this study will be safe for cannabis-experienced participants. The route of administration (vaporization) is common for cannabis self-administration and the doses of both THC and pinene are within the range of what would be expected in real-world cannabis use scenarios. We have submitted an IND application to the FDA for the conduct of this experiment.

c. Justification and safety information if non-FDA approved drugs without an IND will be administered.

N/A

Study Statistics

a. Primary outcome variable.

The primary outcome measure for this study is the total correct on the PASAT (test of working memory).

b. Secondary outcome variables.

Secondary outcome measures include total correct on the International Shopping List Test (test of episodic memory), Reaction Time for Correct Trials on the PASAT, Number Correct on the DSST, self-reported rating of "Trouble With Memory" on the DEQ, and composite score of the Confusion-Bewilderment sub-scale of the POMS.

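### List 1 of the word-list test is held under drug as well as recalled under drug, so its score cannot be read as a test of retrieval alone

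*Combined protocol and SAP*

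**What the plan says.** Section 4a, Study Measures, describes the International Shopping List Test. List 1 comes first: "participants will be shown such a list at baseline (before drug administration". Participants are then "asked to recall items from the list post-drug administration (during peak drug effects". List 2 follows: "Following recall of the initial list, participants will be presented with a new list of 12 items that they will be asked to memorize". Its scoring comes last: "Recall of this second list will be measured at the end of the experimental session (6 hours-post dosing". From this the plan concludes that it can test pinene "at two memory stages: the memory retrieval phase (list 1) and the memory encoding/consolidation phase (list 2".

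Four other places bear on the point:

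- Section 4a, Experimental Drug Exposure, allows 15 minutes for inhalation and sets time zero at its end.
- Section 4a, Post-Drug Administration Procedures: "Episodic memory tests will only be administered at 30 min and 360 min".
- Section 4a, Baseline Assessments, lists "a brief cognitive performance battery including tests of working and episodic memory" before drug, but describes no recall score.
- Study Statistics, item b, names the secondary outcome as "total correct on the International Shopping List Test (test of episodic memory", without saying whether list 1, list 2 or their sum is meant.

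**The concern.** The plan places consolidation with list 2 only. Its own timetable places it with list 1 too, because list 1 must survive dosing and the rise to peak effect before anyone is asked to recall it. If THC lowers list 1 recall and pinene restores it, the plan as worded would report relief of a retrieval deficit. Protection of the stored items during those 30 to 45 minutes would give the same result.

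At stake is a mechanistic conclusion on the trial's only dedicated test of episodic memory. Because the secondary outcome does not name a list, the two scores could also be added together, which would blur the distinction that Study Measures draws between them.

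**Working it through.** The plan gives no figure for this test, so there is none to reproduce. The check is of timing and of what the two scores can identify.

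**Step 1: timeline** (section 4a: Experimental Drug Exposure, Post-Drug Administration Procedures, Study Measures)

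| | Learned | Recalled | Held after dosing starts |
|---|---|---|---|
| List 1 | Before drug | 30 min | 30 min, up to 30 + 15 = 45 min with inhalation |
| List 2 | About 30 min, under drug | 360 min | 360 − 30 = 330 min |

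**Step 2: which stages each score contains.** Let E, C and R be the fractions of placebo performance preserved under drug at encoding, retention/consolidation and retrieval. Assume that they multiply, that C is common to both lists, and that retrieval at 6 h is free of drug effect. Then:

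- list 1 ratio to placebo = C × R (encoding preceded the drug)
- list 2 ratio to placebo = E × C

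That is two equations in three unknowns (rank 2 of 3). Multiply E and R by any k and divide C by k, and both ratios are unchanged. The same algebra applies to THC plus pinene against THC alone.

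**Step 3: illustration.** Assume placebo recall of 9 items on list 1 and 8 on list 2 (the documents give no such figures).

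- Case A, no retention effect: E = 0.75, C = 1, R = 0.80. List 1 = 9 × 1 × 0.80 = 7.2; list 2 = 8 × 0.75 × 1 = 6.0.
- Case B, no retrieval effect: E = 0.9375, C = 0.80, R = 1. List 1 = 9 × 0.80 × 1 = 7.2; list 2 = 8 × 0.9375 × 0.80 = 6.0.

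The planned scores are identical, yet the list 1 deficit is all retrieval in A and all retention in B.

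**Step 4: would a pre-drug list 1 score help?** It contains none of E, C or R, so the rank stays at 2 and retrieval is still not identified. As a covariate it would only reduce residual variance, to 1 − ρ² of its value. For ρ = 0.3, 0.5 and 0.7 that is 0.91, 0.75 and 0.51. The ρ is assumed, and in a crossover it must be the within-person correlation across sessions.

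**Step 5: list 2.** If some retrieval impairment remains at 6 h, the list 2 ratio becomes E × C × R₆ and the combined label also takes in retrieval. Section 4a, Outpatient Discharge, expects effects to have resolved by about 6 h from experience with similar doses, but also provides for participants who are still impaired then.

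**The case against.** The strongest reply is that little of the design is at fault. Several stronger criticisms are tempting, and the documents do not support them.

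- *The schedule cannot test memory stages at all.* Too broad. Because list 1 is learned before drug, encoding is excluded for it. List 2 is learned under drug and scored when effects are expected to be gone, which fits its label.
- *List 2 fails because poor learning cannot be told from later loss.* True as a limit on interpretation, but the plan names encoding and consolidation jointly and never promises to separate them.
- *The lack of a learning score biases list 1.* Learning precedes dosing and session order is randomized, so differences in learning are balanced across conditions in expectation, apart from carryover. The exception is participants who return for the two 15 mg conditions: those sessions necessarily come last, which is a separate question of order.
- *No learning score is taken in any session.* Not established. Baseline Assessments names an episodic memory test, and the restriction to 30 and 360 min stands in the list of post-drug procedures. Study Measures says only that the list is shown. The two need reconciling.
- *Drug is present for most of the list 1 retention interval.* Not derivable. The gap between showing list 1 and starting inhalation is not given, and other baseline assessments may fall within it.

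It is also fair to say that this is one interpretive sentence about a secondary outcome. What survives is the retrieval label, which attributes to list 1 something its timing does not give.

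**Conclusion.** The concern holds for the list 1 label. A list 1 effect is an effect on retention plus retrieval of material learned before drug, after at least 30 and up to about 45 minutes under drug. The planned scores cannot divide it: in the illustration the same pair of scores arises with no retention effect and with no retrieval effect. This follows from the schedule; the illustrative recall values and the multiplicative form are assumptions that only make it visible.

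The list 2 label stands as a joint one, provided that retrieval at 6 h is drug-free. The lists also differ in delay, content and order, so a direct comparison between them would be confounded; the plan does not state one. The contrasts of THC with and without pinene remain valid within each list, and neither the PASAT primary outcome nor the target of 20 completers is affected.

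A reader might infer that the word-list outcome is invalid or should be dropped. It need not be; only its interpretation has to be narrowed.

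**What to change.** 1. **Section 4a, Study Measures.** Replace the stage claim. Suggested wording: list 1 measures the drug effect on retention plus retrieval of material learned before drug; list 2 measures learning under drug plus retention to 6 h, assuming that retrieval at 6 h is free of drug effect; no conclusion specific to retrieval will be drawn.
2. **Study Statistics, item b.** Replace the single total with two outcomes that are not summed: list 1 correct at 30 min and list 2 correct at 360 min.
3. **Section 4a, Baseline Assessments and Study Measures.** State whether list 1 recall is scored before drug. If such a score exists, it may be used as a list 1 covariate, for precision only.

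Items 1 and 2 need text changes only and apply to data already collected. The cost is the retrieval-specific claim and one more secondary outcome (six instead of the five now listed).

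Immediate recall should not be added now. For list 2 it would identify retrieval in the simple model (0.75 × 0.80 = 0.60 of placebo in case A, 0.9375 × 1 = 0.94 in case B), but only if C is the same for both lists. That recall would take place under drug, so any rehearsal benefit could differ by condition and distort the 360-min score, and a proportion retained would have a drug-affected denominator. It would also change the task for only part of the sample: 13 participants had been randomized when the 15 mg dose was added, against a target of 20 completers.
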